5.3 DOSE REGIMEN.....	19
5.4 TREATMENT COMPLIANCE.....	20
6. STUDY MEASUREMENTS	21
6.1 ULCER ASSESSMENT	21
6.2 PHYSICAL EXAMINATION AND VITAL SIGNS.....	21
6.3 LABORATORY EXAMINATION	21
6.4 STANDARD-OF-CARE PROCEDURES	22
7. STUDY SCHEDULE	23
7.1 SCREENING VISIT	23
7.2 INITIAL PHASE VISIT (ONLY FOR APPLICABLE SUBJECTS)	24
7.3 RANDOMIZATION VISIT	24
7.4 EVALUATION VISITS DURING TREATMENT PERIOD IN VISITS 4 TO 11	24
7.5 FOLLOW-UP VISITS	25
7.6 FINAL VISIT.....	25
8. ADVERSE EVENTS.....	26
8.1 DEFINITIONS	26
8.2 AE/SAE INTENSITY AND RELATIONSHIP ASSIGNMENT	26
8.3 COLLECTING, RECORDING AND REPORTING OF ADVERSE EVENTS	28
9. DATA ANALYSIS	29
9.1 DATA QUALITY ASSURANCE	29
9.2 CLINICAL DATA MANAGEMENT.....	29

10. SAMPLE SIZE AND STATISTICAL METHODS	30
10.1 DETERMINATION OF SAMPLE SIZE	30
10.2 STATISTICAL AND ANALYTICAL PLANS	30
11. ETHICAL CONSIDERATIONS	32
11.1 INFORMED CONSENT	32
11.2 IRB REVIEW	32
11.3 CONFIDENTIALITY OF DATA AND PATIENT RECORDS	32
12. PUBLICATIONS	34
13. RETENTION OF TRIAL DOCUMENTS.....	34
14. REFERENCES	35

PROTOCOL SUMMARY

Full Title	A Randomized, Double-Blind, Vehicle-controlled, Parallel, Phase II Study to Evaluate Efficacy and Safety of CSTC1 in Patient with Diabetic Foot Ulcers
Short Title	CSTC1 for Diabetic Foot Ulcers Phase II Study
Project No	CSCT1-01
Study Phase	Phase II
Sponsor	Charsire Biotechnology Corp.
Objectives	To evaluate the efficacy and safety of CSTC1 in patient with diabetic foot ulcers
Study Design	Randomized, double-blind, vehicle-controlled, multiple center, parallel study
Study Population	Subject aged at least 20 years old in Taiwan diagnosed with diabetic ulcer (which is selected by investigator and defined as the target ulcer) on the foot that not healing for at least 4 weeks
Number of Subjects	The sample size is determined to be 80 versus 20 subjects (4:1 ratio) for Treatment versus Control groups, 100 subjects in total. To ensure the completion of 100 evaluable subjects, around 125 subjects will be recruited.
Study Product, Dose, Route, Regimen	CSTC1 [REDACTED] [REDACTED] topical application, 2 times daily
Duration of Administration	12 weeks of treatment or confirmed complete ulcer closure, whichever comes first, and up to 12 weeks of post-treatment follow-up for subject with confirmed complete ulcer closure after at most 12 weeks of treatment; Subjects failed to achieve complete ulcer closure will be arranged for 4 weeks of safety follow-up
Subject Assignment	Subjects who meet all eligible requirements for entry into the study will be randomized into one of the treatment group or vehicle control group in 4:1 ratio as shown below: Treatment Group: CSTC1 Control Group: Matched vehicle
Subjects Inclusion Criteria	A subject is eligible for the study if all of the following apply: 
 1. With either gender aged at least 20 years old 2. With at least one diabetic foot ulcer (including ulcers on the lower legs) and not healing for at least 4 weeks. The largest diabetic foot ulcer will be selected as target ulcer. If two or more ulcers have the largest size, the one with worst grade will be selected. If two or more ulcers have the largest size and grade, the one with longest duration will be selected.

	
 3. The target ulcer is classified as grade 1 to 2 ulcer according to modified Wagner system and with ulcer size of 1cm² to 50 cm² 4. The target ulcer should be confirmed without active infection 5. Subject should be free of any necrosis or infection in soft and bone tissue; 6. Subject has signed the written informed consent form
Subjects Exclusion Criteria	
Any subject meeting any of the exclusion criteria will be excluded from study participation.
 
 1. With active osteomyelitis 2. With target ulcer size decreased by at least 30% after at least 2 weeks of standard-of-care-only period or any other recorded regular therapy before Randomization visit 3. With poor nutritional status (albumin < 2g/dl), poor diabetic control (HbA1c > 12%), anemia (hemoglobin < 8 g/dL), a leukocyte counts < 2,000/mm³, abnormal liver function (AST, ALT>3 x upper limit of normal range) 4. Requiring treatment with systemic corticosteroids, immunosuppressive or chemotherapeutic agents within 28 days prior to Screening visit 5. Presence of necrosis, purulence or sinus tracts that cannot be removed by debridement 6. Receiving revascularization surgery or endovascular therapy performed <8 weeks before entry in the study 7. With known or suspected hypersensitivity to any ingredients of study product and vehicle 8. With coronary heart disease with myocardial infarction, coronary artery bypass graft (CABG), or percutaneous transluminal coronary angioplasty (PTCA) within 3 months prior to study 9. Pregnant or lactating or premenopausal with childbearing potential but not taking reliable contraceptive method(s) during the study period 10. Enrollment in any investigational drug trial within 4 weeks before entering this study 11. With any uncontrolled illness judged by the investigator that entering the trial may be detrimental to the subject
Primary Endpoint	
Efficacy:
 
The incidence of complete ulcer closure during up to 12 weeks of treatment period
 
Complete ulcer closure is defined as 100% skin re-epithelialization without drainage or dressing requirements confirmed at two consecutive study visits 2 weeks apart. Subjects with complete ulcer closure at week-12 visit and confirmed at week-14 visit will be considered as success.

Secondary Endpoints Efficacy:

1. The ulcer closure time
Defined as the time to complete ulcer closure
2. The complete ulcer closure rate
The proportion of subjects with complete ulcer closure at each post-treatment visit
3. Percentage change in ulcer size for each post-treatment visit
Calculated as (Ulcer size at post treatment visit - Ulcer size at baseline)/(Ulcer size at baseline)

Safety:

1. Adverse event incidence
2. Change in physical examination results
3. Net change from baseline in laboratory test results (include hemoglobin, hematocrit, RBC, platelet, WBC with differential counts, HbA1c, fasting glucose, AST, ALT, creatinine and BUN)
4. Net change from baseline in vital signs

Statistical Analysis Analysis population

Three data sets will be introduced for statistical analysis.

Intent-to-treat (ITT) population:

- All randomized subjects who have received at least one dose study medication.

Per-protocol (PP) population:

- A subset of ITT population
- Fulfill all inclusion and exclusion criteria
- Dosed with at least 8 weeks study drug or with early confirmed complete ulcer closure AND with at least 70% treatment compliance
- Did not receive any prohibited treatment during treatment period
- With any post-treatment assessment relevant to efficacy endpoint up to end of dosing period

Efficacy endpoints will be analyzed on ITT and PP population.

Demographics, baseline characteristics, and safety endpoints will be analyzed on ITT population. Conclusion of efficacy will be made according to the result of ITT population analysis.

Analysis

Demographics and baseline characteristics will be summarized for each group by using descriptive statistics.

The efficacy endpoints will compare the CSTC1 group with vehicle group. Incidence of ulcer closure and ulcer closure rate at endpoint will be analyzed with Cochran-Mantel-Haenszel test (CMH test). Ulcer closure time will be estimated by using Kaplan-Meier methods and compared between groups by using log-rank test. Percentage change in ulcer size will be analyzed by using Analysis of variance (ANOVA) model with treatment group and center as factors. Further efficacy analyses with ankle brachial index (ABI) (<0.7 or not) as stratification may be performed if necessary.

For safety analyses, adverse events will be reported by treatment groups and by physiological systems as appropriate. Incidence of adverse events between treatments will be analyzed by CMH test. Changes in physical examinations will be displayed for each individual system. Net changes from pre-treatment laboratory test results and vital signs will be analyzed by descriptive statistics.

Additionally, descriptive statistics will be provided for all of the endpoints. Frequency table will be provided for categorical data, while mean, standard deviation, maximum, minimum, median, inter-quartile range (IQR), and 95% two-sided confidence interval will be calculated for continuous measurements. In addition, endpoints of time to event will be presented by using the life table and Kaplan-Meier plot. The Kaplan-Meier estimates will also be provided for these time-to-event endpoints.

All treatment group comparisons will be conducted with significance level of 0.05.

SCHEDULE OF ASSESSMENTS

	Screening ¹	Initial ² Phase	Randomization ³ (Baseline)	Dosing/Observation								Follow-up			
	1	2	3	4	5	6	7	8	9	10	11 ¹¹	12	13	14	15
Week relative to Baseline visit	-3~-2	-2~0	0	1	2	3	4	6	8	10	12	14	16	20	24
Visit Window (days)	NA	±4	NA	±4	±4	±4	±4	±4	±4	±4	±4	±4	±4	±4	±4
Informed consent signed and given	X														
Screening number assignment	X														
Randomization			X												
Demographic data & medical history	X														
Inclusion and exclusion criteria	X		X												
Pregnancy test for applicable subjects	X										X				
Ulcer Evaluation ⁴	X		X	X	X	X	X	X	X	X	X	X	X	X	X
Vital signs	X		X	X	X	X	X	X	X	X	X	X	X	X	X
Physical examinations	X		X	X	X	X	X	X	X	X	X	X	X	X	X
Ankle Brachial Index ⁵	X														
Laboratory test: hemoglobin, hematocrit, RBC, platelet, WBC with differential counts, HbA1c, fasting glucose, AST, ALT, creatinine and BUN, albumin	X ⁶		X ⁷								X ⁸				
Record concomitant medication(s)	X	X	X	X	X	X	X	X	X	X	X	X	X	X	X
Standard of Care		X	X	X	X	X	X	X	X	X	X				
Record adverse events (AE) ⁹	X	X	X	X	X	X	X	X	X	X	X	X	X	X	X
Dispense trial medication			X	X	X	X	X	X	X	X					
Returned medication count				X	X	X	X	X	X	X	X				
Diary Dispensing			X												
Diary Return				X	X	X	X	X	X	X	X				
Complete exit form													X		X
Dismiss subject ¹⁰													X		X

Footnote:

- 1: Could be on the same day as the first day of Initial Phase or randomization visit if subject's Initial Phase can be waived
- 2: Can be waived if subject's diabetic foot ulcer(s) has been treated for at least 2 weeks, and is still eligible to enter this study
- 3: Could be on the same day as the last day of Initial Phase
- 4,10: Subjects with confirmed complete ulcer closure up will be arranged for ulcer evaluation for follow-up period; Subjects not with complete ulcer closure will take 4 weeks of safety evaluation

- 5: The two blood pressures for calculating ABI, ankle and brachium, should be measured on the same side (left to left, right to right) and should be on the same side of target diabetic foot ulcer. However, the blood pressures of brachium may not be available for some patients. For such case, investigator is suggested trying to measure pressure of brachium of another side.
- 6: Test results within 14 days before Screening visit are acceptable; HbA1c test result within 28 days can be accepted. Albumin test will only be done at Screening and Randomization visits
- 7: Test results within 28 days before Randomization visit are acceptable
- 8: Test results within time window are allowed
- 9: AE should be recorded since informed consent is signed
- 11: For subject who has been confirmed complete closure before week-12 visit should be arranged for visit 11 assessment.

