2.2.2 Secondary efficacy endpoints

1. The ulcer closure time

Defined as the time to complete ulcer closure

2. The complete ulcer closure rate

The proportion of subjects with complete ulcer closure at each post-treatment visit

3. Percentage change in ulcer size for each post-treatment visit

Calculated as (Ulcer size at post treatment visit - Ulcer size at baseline)/(Ulcer size at baseline)

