3.2 Inclusion Criteria

A subject is eligible for the study if all of the following apply:

1. With either gender aged at least 20 years old
2. With at least one diabetic foot ulcer (including ulcers on the lower legs) on the foot and not healing for at least 4 weeks. The largest diabetic foot ulcer will be selected as target ulcer. If two or more ulcers have the largest size, the one with worst grade will be selected. If two or more ulcers have the largest size and grade, the one with longest duration will be selected.
3. The target ulcer is classified as grade 1 to 2 ulcer according to modified Wagner system and with ulcer size of 1cm² to 50 cm²
4. The target ulcer should be confirmed without active infection.
5. Subject should be free of any necrosis or infection in soft and bone tissue;
6. Subject has signed the written informed consent form

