4.2 Randomization and Blinding

Permuted block randomization method will be applied to generate randomization codes. Each randomization number will be assigned to individual subject according to the time-sequence for screened subject becoming eligible.

Both CSTC1 and its matched vehicle will be prepared to be identical in all aspects to achieve the double-blind purposes. All subjects will take proper amount of CSTC1 or CSTC1 matched vehicle per application to ulcer area.

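### The Summary names no baseline-area adjustment for the primary CMH test or the log-rank test; if area predicts closure and redacted section 10.2.2 does not adjust for it, some power is lost and a chance size imbalance goes uncorrected

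*Combined protocol and SAP*

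**What the plan says.** The Protocol Summary (Statistical Analysis) gives the closure test as "Incidence of ulcer closure and ulcer closure rate at endpoint will be analyzed with Cochran-Mantel-Haenszel test (CMH test" and the closure-time analysis as "Ulcer closure time will be estimated by using Kaplan-Meier methods and compared between groups by using log-rank test". Neither sentence names a stratum or covariate.

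The same paragraph does name factors for other analyses. The analysis of size change reads "Percentage change in ulcer size will be analyzed by using Analysis of variance (ANOVA) model with treatment group and center as factors". The only baseline prognostic factor named for efficacy is optional: "Further efficacy analyses with ankle brachial index (ABI) (<0.7 or not) as stratification may be performed if necessary".

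On ulcer size, section 3.2 requires: "The target ulcer is classified as grade 1 to 2 ulcer according to modified Wagner system and with ulcer size of 1cm² to 50 cm²". Section 7.3 includes an ulcer evaluation at the Randomization visit. Section 2.2.2 uses baseline size as the denominator of percentage change: "Calculated as (Ulcer size at post treatment visit - Ulcer size at baseline)/(Ulcer size at baseline". The value should therefore be on file for every randomized subject.

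Section 4.2 specifies permuted blocks and states: "Each randomization number will be assigned to individual subject according to the time-sequence for screened subject becoming eligible". It names no stratification factor. Section 3.1 sets 80 v 20 evaluable subjects, with about 125 recruited. Sections 10.1 (sample size) and 10.2.2 (efficacy analyses) are redacted.

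**The concern.** The primary endpoint is full re-epithelialization of the target ulcer within 12 weeks, and the first secondary endpoint is the time to it. A larger ulcer has more surface to cover in the same time, so area is a natural candidate predictor of both. Two things are at stake if it is left out.

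- **Power.** A test that ignores a strong predictor of a binary or time-to-event outcome is less sensitive than one stratified by it.
- **Reading of the one trial that is run.** With 4:1 allocation the vehicle arm is small, and by chance its ulcers may be clearly larger or smaller than those on CSTC1. Part of any closure difference could then be a size difference. Section 2.1.2 says that the results may go into a new drug application dossier, where this question would be a fair one. A pre-specified adjustment answers it better than a post hoc one.

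**Working it through.** **1. Figures from the plan.** Area range: 50/1 = 50-fold, or log2(50) = 5.64 doublings. Arms at 4:1: 100 subjects give 80:20, and 125 give 100:25. 100/125 = 0.80, so a 20% loss is implied, though not stated. The 80:20 itself cannot be reproduced, because closure rates and power are redacted in 10.1.

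**2. Chance imbalance in mean log area.** The SD of the between-arm difference, in SD units of log area, is √(1/n₁ + 1/n₀).

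| Arms | SD of difference | P(beyond ±0.25 SD) | P(beyond ±0.5 SD) |
|---|---|---|---|
| 80:20 | √(1/80 + 1/20) = 0.250 | 32% | 4.6% |
| 100:25 | √(1/100 + 1/25) = 0.224 | 26% | 2.5% |

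With 1:1 allocation and the same totals, the SDs would be 0.200 and 0.179.

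**3. Assumptions for power.** The documents give no closure rates, no distribution of area and no strength of association, so all three are assumed and the last two are varied. Marginal closure is 30% v 63%. Area is either log-uniform on 1 to 50 cm² or truncated lognormal with median about 4 cm². Closure is logistic in log area, with an odds ratio (OR) per doubling of 1.0 to 0.5. Tests are two-sided at 0.05; the Summary gives 0.05 without stating sides.

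**4. Primary CMH test, tertile strata v no strata.** Ranges run over both area distributions and both arm sizes.

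| OR per doubling of area | Change in power from stratifying |
|---|---|
| 1.0 (no association) | about -1 point (up to -1.4) |
| 0.8 | about 0 |
| 0.65 | +1 to +2 |
| 0.5 | +3 to +7 |

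Absolute figures near the upper end: log-uniform area, correlation of area with closure 0.43 (OR about 0.51 per doubling). Power goes from 86.2% to 91.5% at 100:25 (+5.3) and from 77.4% to 84.0% at 80:20 (+6.6). A separate run with 30% v 65% at 80:20 and OR 0.5 gave 82.7% to 85.2% (lognormal, +2.5) and 82.8% to 88.9% (log-uniform, +6.1).

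**5. Log-rank test.** 80:20, marginal closure 30% v 65%, closure read on the visit grid, strata split at the median area. The pairs are lognormal; log-uniform.

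| HR per doubling | Unstratified | Stratified | Gain (points) |
|---|---|---|---|
| 1.0 | 81.1%; 79.7% | 80.6%; 79.2% | -0.5; -0.5 |
| 0.8 | 80.2%; 80.6% | 80.8%; 82.2% | 0.6; 1.6 |
| 0.65 | 80.8%; 81.8% | 83.5%; 87.8% | 2.7; 6.0 |
| 0.5 | 80.8%; 84.3% | 87.7%; 95.1% | 6.9; 10.8 |

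Monte Carlo standard error is about 0.5 points. With tertiles in place of the median split, the gains at HR 0.5 are 89.0 - 80.8 = 8.2 and 96.8 - 84.3 = 12.5 points; with no association the loss is 1.2 and 1.1 points.

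**6. Error rates.** Over all trials with no treatment effect (80:20), the unstratified CMH rejects in 4.7% to 5.1%. The picture changes once the imbalance is known. In trials where CSTC1 happens to get ulcers smaller by more than 0.25 SD, the one-sided false-positive rate in its favour (nominal 2.5%) is 2.6% to 3.3% at OR 0.8, 4.4% to 4.5% at 0.65 and 4.8% to 6.4% at 0.5. Median strata bring these to 2.1% to 2.9% at OR 0.8 and 0.65, and to 2.5% to 3.0% at 0.5. In the mirror case, with larger ulcers on CSTC1 and OR 0.5, power is 62% to 69% unstratified and 82% to 85% stratified.

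**The case against.** The strongest objection is the redaction. The quoted sentences come from a synopsis. CMH is built to take strata, and 10.2.2, where strata and covariates would be set, cannot be read. A reader might infer that the plan omits area; the documents do not support that, and the point has to be confined to the Summary. This stands.

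A reader might also infer that both tests lose power as a matter of course. That does not follow either. No readable text says how strongly area predicts closure or how area is distributed within the 1 to 50 cm² limits. The larger gains need a steep relation: at a correlation of 0.43 under log-uniform area, vehicle closure falls from 70% at 1 cm² to 5% at 50 cm². If ulcers cluster at smaller sizes, the gain is roughly halved. This stands too, and is why the sizes are given as a range that starts at a small loss.

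A third tempting reading is that chance imbalance invalidates the unstratified test. It does not: randomization already allows for it, and overall type I error stays at about 5%. What remains is the conditional problem in step 6, which is real only if area is prognostic. Nor should the log-rank choice be called biased. It is a test, and the Summary names no hazard-ratio estimate.

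The objection does not remove the textual facts. The Summary names factors for the ANOVA and an optional ABI stratification, but area for neither closure test, and section 4.2, which shows no visible redaction, names no balancing factor.

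**Conclusion.** The point holds in conditional form. As named in the Summary, neither the primary CMH test nor the log-rank test uses baseline ulcer area, although area may differ 50-fold, is measured at randomization and is not balanced by any stated design factor. If area predicts closure and 10.2.2 is silent, the cost on the primary test is between nothing and about 7 points of power over OR 1.0 to 0.5 per doubling, and on the log-rank test up to about 11 points. In addition, a size imbalance against 20 to 25 vehicle subjects would go uncorrected in the trial at hand. These sizes rest on the assumed closure rates, area distributions and prognostic strengths; only the area limits, arm sizes and significance level come from the documents. This is a modest, inexpensive gain in efficiency and interpretability. It is not a flaw in the validity of the tests.

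**What to change.** First check 10.2.2. If it already uses baseline area in both tests, the only change needed is to say so in the Summary.

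Otherwise, state in the Summary and in 10.2.2 that the primary CMH test and the log-rank test are both stratified by target-ulcer area at the Randomization visit, in three classes cut at the pooled tertiles and fixed before unblinding. Keep the unstratified tests as sensitivity analyses.

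If 10.2.2 already stratifies the CMH test by center, crossing center with area would give sparse cells. In that case pre-specify one primary analysis that carries both center and log area, for example the score test for treatment from a logistic model, and do not leave the choice open.

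The change is wording only, made before unblinding, with no new data, visits or subjects. The price is about 1 point of power on the primary test (up to about 1.4 at 80:20) if area turns out not to predict closure.

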3. STUDY POPULATION

3.1 Subjects Enrollment

The sample size is determined to be 80 versus 20 subjects (4:1 ratio) for Treatment versus Control groups, 100 subjects in total. To ensure the completion of 100 evaluable (= per-protocol) subjects, around 125 subjects will be recruited. All of the subjects will be recruited in Taiwan. Any subject fulfills all of the recruitment criteria will be screening and/or randomized into the study.

Re-screening for patient's eligibility will be allowed if the patient is willing to participate in the study and one of the following conditions meets:

1. If a patient consents to participate and meets the eligibility criteria but a delay occurs in starting to participate in due to certain change in situation such that some measurement relevant to eligibility became invalid owing to the delay
2. If the cause of screen failure has now resolved or adequately treated such that patient's medications have now stabilized

In these situations, if randomization has not occurred;

1. A new CRF will be used
2. A new Screening number will be assigned to the person
3. The person will be marked as having been re-screened on both the CRF and the site master list
4. The patient needs to sign a new ICF as part of the screening procedure.

It is not appropriate to re-screen a patient if he/she has previously failed to meet the eligibility criteria and no further changes or treatments have been able to indicate that the patient may be suitable.

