7.3 Randomization visit

(Day 0)

1. Re-confirm eligibility of subject
2. Ulcer evaluation
3. Vital signs
4. Perform physical examinations
5. Obtain blood samples for hematologic and biochemical tests (The tests can be waived if the tests have been performed within past 28 days)
6. Assign randomization number to eligible subject
7. Record changes on concomitant medication(s)
8. Dispense material of standard-of-care
9. Record adverse event(s)
10. Dispense trial medication
11. Dispense diary to patient

7.4 Evaluation visits during treatment period in visits 4 to 11

(Weeks 1, 2, 3, 4, 6, 8, 10, 12 with time window ± 4 days)

Subjects confirmed complete ulcer closure before week-12 visit will be arranged for post-treatment follow-up.

1. Ulcer evaluation
2. Vital signs
3. Perform physical examinations
4. Obtain blood samples for hematologic and biochemical tests (will only be performed at week 12 visit or when subject complete the treatment period)
5. Record changes on concomitant medication(s)
6. Dispense material of standard-of-care

7. Record adverse event(s)
8. Collect unused treatment medication(s) (which is dispensed at prior visit)
9. Dispense trial medication (excluding week 12 visit)
10. Collect and check diary (which recorded from previous visit)
11. At week-12 visit only, perform pregnancy test for female with childbearing potential

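### The Summary's model for percentage change in ulcer size omits baseline ulcer area, a covariate already measured that would cost one degree of freedom

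*Combined protocol and SAP*

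**What the plan says.** The Protocol Summary (Statistical Analysis) gives the model: "Percentage change in ulcer size will be analyzed by using Analysis of variance (ANOVA) model with treatment group and center as factors". It adds: "All treatment group comparisons will be conducted with significance level of 0.05". The only other adjustment it names is an optional analysis stratified by ankle brachial index.

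Section 2.2.2 defines the endpoint, for each post-treatment visit, as the change divided by the starting value: "Calculated as (Ulcer size at post treatment visit - Ulcer size at baseline)/(Ulcer size at baseline". Section 7.3 lists "2. Ulcer evaluation" at the Randomization visit, so the starting value is in hand for every randomized subject. Section 3.2 admits target ulcers "with ulcer size of 1cm² to 50 cm²".

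On design, section 4.2 says "Permuted block randomization method will be applied to generate randomization codes" and mentions no stratification by ulcer size. Section 3.1 states: "The sample size is determined to be 80 versus 20 subjects (4:1 ratio) for Treatment versus Control groups, 100 subjects in total". It puts recruitment at around 125.

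The text on secondary endpoints in section 10.2.2 is redacted in the public copy, so this point concerns the Summary only.

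**The concern.** Dividing by baseline area is not the same as adjusting for it. The ratio removes dependence on starting size only if the expected proportional change is the same for a 1 cm² ulcer and a 50 cm² ulcer. If large ulcers shrink proportionally less, or close less often, that variation stays in the residual error. A covariate would remove the linear part of it.

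What is at stake is precision, not validity. Randomization keeps the unadjusted comparison unbiased, and the primary closure analysis does not use this model. But the vehicle arm is small, and nothing readable in the design balances ulcer size between arms.

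A separate and smaller point arises from the 4:1 allocation. The ANOVA pools the variance over both arms, and the larger arm dominates the pooled estimate. If the arms differ in spread, the standard error is wrong. The covariate does not correct that.

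**Working it through.** **The plan's own figures.** No power, SD, effect size or correlation is readable for this endpoint, so there is no figure to reproduce. The 80:20 split cannot be derived either, because section 10.1 is redacted. The recruitment figure equals 100/(1 - 0.20) = 125 only if 20% dropout is assumed.

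**Inputs from the documents.** Allocation 80:20 evaluable, or 100:25 if 125 are recruited at 4:1; significance level 0.05; baseline area 1 to 50 cm².

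**Assumed.** Two-sided tests, 5 centers, log area uniform from log 1 to log 50, and the effect sizes, SDs and correlations below.

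**1. Cost in degrees of freedom.** Residual df = N - 2 - (centers - 1), less 1 for one linear covariate.
- N = 100: 94 falls to 93; critical t goes from 1.9855 to 1.9858.
- N = 125: 119 falls to 118; critical t goes from 1.9801 to 1.9803.

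**2. Closed-form power, 80:20, difference 0.6 SD.** SE = √(1/80 + 1/20) = 0.25, so the noncentrality is 0.6/0.25 = 2.40 and ANOVA power is 66.1%. With the covariate, the residual variance is multiplied by 1 - ρ² and the expected variance inflation is 1 + 1/(93 - 1) = 1.011. At ρ = 0.3 the noncentrality is 2.40/√(0.91 × 1.011) = 2.50 and power is 69.7%. At ρ = 0, 0.1, 0.2, 0.4 and 0.5, power is 65.6, 66.1, 67.4, 73.2 and 77.9%. Break-even is near ρ = 0.1.

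**3. Simulation, normal outcome.** Difference 16.5, SD 30 (0.55 SD), 20,000 runs per cell.

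| Residual correlation | ANOVA, 100:25 | + log area, 100:25 | Change, 100:25 | Change, 80:20 |
|---|---|---|---|---|
| 0 | 67.7% | 67.4% | -0.3 | -0.5 |
| 0.2 | 68.7% | 70.0% | +1.3 | +1.5 |
| 0.3 | 68.8% | 72.3% | +3.5 | +3.7 |
| 0.5 | 68.8% | 80.5% | +11.7 | +12.2 |

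With 10 centers the changes are -0.4, +3.4 and +12.0 at correlations 0, 0.3 and 0.5. If the true relation is to raw area or a step at 10 cm², the log term still gains 2.5 to 2.8 points at 0.3 and 8.0 to 9.3 at 0.5.

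**4. Simulation with closed ulcers at -100%.** Closure 60 vs 30%; non-closers have mean -40, with SD 30 (normal) or SD 45 (log-normal, skewed); 12,000 runs per cell; 100:25.

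| Fall in closure odds per SD of log area | Normal: ANOVA → + log area | Skewed: ANOVA → + log area |
|---|---|---|
| 1 (none) | 60.5 → 60.2% | 48.2 → 48.0% |
| 1.65-fold | 60.5 → 61.5% | 48.2 → 48.9% |
| 2.2-fold | 60.0 → 63.2% | 48.2 → 50.0% |
| 3.3-fold | 59.9 → 66.9% | 48.5 → 52.6% |

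A second set of spike runs gave -0.7, +1.1, +3.0 and +5.2 points. Over all runs the worst loss was 0.7 point.

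**5. Chance imbalance.** P(difference over 0.3 SD) = 2(1 - Φ(0.3/SE)).
- 100:25, SE 0.224: 18%.
- 80:20, SE 0.250: 23%.
- 1:1 with 125, SE 0.179: 9%.

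This is the same loss of precision seen from another side, not an added one.

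**6. Unequal spread.** Take CSTC1:vehicle SDs of 30:60 at 100:25. The true SE is √(900/100 + 3600/25) = √153 = 12.4. The pooled variance is (99 × 900 + 24 × 3600)/123 = 1427, so the pooled SE is √(1427 × 0.05) = 8.4. The test statistic is about 1.46 times too variable, and type I error is near 2(1 - Φ(1.98/1.46)), about 17.5%. Simulated type I error:

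| SD ratio | Pooled ANOVA | Covariate + HC3 |
|---|---|---|
| 30:40 | 9.7% | 4.7% |
| 30:45 | 12.0% | 5.2% |
| 30:60 | 17.9% | 5.1% |
| 45:30 | 1.3% | 4.0% |

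Adding the covariate leaves the pooled error rates unchanged.

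**7. Price of HC3 against the same covariate model.** Power falls by 2.5 to 4.3 points at equal variances, 5 to 8 with the closure spike, and 9 to 13 with skewed non-closers. It falls by 18 to 26 if treatment also shrinks the ulcers of non-closers; there the pooled intervals cover only 82 to 88%, so part of the gap is pooled anti-conservatism. HC3 does not protect under strong skew with unequal spread: at 45:90 the error is 11.3%, against 11.0% pooled.

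**The case against.** The evidence is one sentence in a summary. The detailed text is redacted and may already contain the covariate, in which case only an editorial mismatch remains. ANOVA with treatment and center is a legitimate prespecified model for a Phase II secondary endpoint, and nothing in the documents is contradicted. This stands, and it limits the point to the Summary and to a low severity.

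The largest gains are also the least realistic. In the closure-spike model, even a 3.3-fold fall in closure odds per SD of log area implies a within-arm correlation of only about 0.34 to 0.41 with normal non-closers, or 0.27 to 0.35 with skewed ones (area acting only through closure). This stands too: the gain of about 12 points at 0.5 is an upper extreme, and the spike results are the better guide. The 1 to 50 cm² range is an eligibility limit, not a distribution, and does not by itself show that area is prognostic.

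The unequal-spread material is a different issue. Nothing in the documents suggests that the arms differ in SD, HC3 fails in some skewed cases, and a sensitivity analysis at each of 12 post-baseline visits in two populations could add 24 results. That is a fair argument against making HC3 the main analysis, and it is not proposed as such. None of it removes the case for the covariate, whose cost is at most about half a point of power and whose value is already recorded.

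**Conclusion.** The concern holds for the model as the Summary states it. Baseline ulcer area is measured, spans up to a 50-fold range by eligibility, and is missing from the analysis of percentage change. Adding it costs one degree of freedom and 0.2 to 0.7 point of power if area is not prognostic. If area is prognostic, the gain at 100:25 is roughly 1 to 7 points in the closure-spike runs and up to about 12 in the normal model.

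These sizes rest on assumed SDs, effects, correlations, closure rates and number of centers. The real gain cannot be known from the documents. Confidence is medium, and the point is one to consider: the comparison is not biased and the primary endpoint is unaffected.

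**What to change.** Keep treatment group and center in the model for percentage change in ulcer size, and add log baseline ulcer area as a covariate in the main analysis. Fix this before unblinding, since a covariate added later would look data-driven. If section 10.2.2 already names the covariate, bring the Summary into line with it.

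Prespecify the same model with HC3 standard errors as a sensitivity analysis only. The main test stays with the covariate model, so the power cost of HC3 does not fall on the main result. Where the two disagree, report both and read the result with caution.

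The cost is one sentence of analysis text, one degree of freedom, no new data, and one further line of output per visit in each population analyzed.
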